Temperature ^f		Measure and record temperature three times daily until afebrile for 14 days, then once daily in the evening until afebrile for 28 days							
Pulse oximetry ^f	Х	Twice daily through day 15			Thrice weekly through day 29				
Weight	Х								Х
Questionnaire and diary	Х	Every evening days 2-28; days 1, 3, 5 weekly thereafter ^g							
ECG ^h	Х			Х	Х		Х		
Nasal mid-turbinate (NMT) swab for SAR-CoV-2 PCR ⁱ	Х			Х	Х		Х		Х
CBC, biochem profile ^j , D-dimer, INR, PTT				Х	Х		Х		Х
CRP, D-dimer, troponin, ferritin	Х			Х	Х		Х		Х
Serum IgG and IgM antibodies to SARS-CoV-2	Х							С	Х
Alpha-1-antitrypsin and G6PD testing								Ck	X ^k
Study medication		<							
Adverse events ^I			Х	Х	X	Х	Х	Х	Х
Concomitant medications	Х		Х	Х	Х	Х	Х	Х	Х

Abbreviations: BL: Baseline; EOS: end of study; EOT: end of treatment

^aEnd of treatment visit, regardless of actual study day. Should generally be day 15, the day AFTER last dose of study medication.

^bEnd of study visit: generally day 57±4 from start of treatment, regardless of duration of treatment. If patient discontinues study participation prior to then, end of study procedures should be carried out, if possible, at the time of discontinuation from study, even if earlier than day 53.

^cType of contact/location: F: in facility: emergency department, clinic, COVID-19 special facility; H: home visit; H/F: option for either home or facility visit; T: televisit, either phone or video. Note: additional televisits may be arranged as needed. If patient returns to medical facility for outpatient visit, if possible, relevant procedures and tests should be performed at that time.

At all clinic and home health visits, temperature, pulse, respiratory rate, blood pressure, pulse oximetry and ECG measurements will be performed. Home health staff will obtain all vital signs independently of patient measurements, to verify that data are being collected accurately.

^dWithin 3 days prior to planned start of treatment: initial procedures include signing informed consent, review of medical history, review of documentation of COVID-19 disease and source/exposure, if available, height (measured or per patient), pregnancy test for women of childbearing potential, as detailed in section 5.2. When feasible, BL and day 1 procedures, i.e., start of treatment, should be completed on the same day.

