Swab at baseline (confirmatory of pre-study test, if a prior swab obtained). At baseline, a rapid PCR or antigen test for diagnosis will be performed on site (if PCR or antigen has not been obtained within 5 days of planned start of treatment), and a quantitative PCR, the same as will be used on other study days, also taken and sent to the central laboratory. Then days 8, 15, 29 and 57. Procedure shown in Appendix 1. The baseline specimen will also be sequenced.

Biochemistry profile to include, at a minimum, albumin, alkaline phosphatase, ALT, AST, bilirubin (total). Bicarbonate, BUN, calcium, chloride, creatinine, glucose, LDH, potassium, sodium, and total protein.

^kTests for serum alpha-1-antitrypsin level and whole blood glucose-6-phosphate dehydrogenase (G6PD) deficiency, both to be taken at the day 57 visit only, are optional and will require a separate consent (C), which should be obtained at the day 43 telemedicine visit.

Adverse events and concomitant medications will be recorded by the patient or caregiver daily (first 4 weeks) or d1, 3 and 5 each week (weeks 5-8) in their diary. These will be reviewed at each home or clinic visit or televisit and entered by study staff in the appropriate eCRF forms.

List of Abbreviations

AE Adverse Event

ALT Alanine Aminotransferase
AST Aspartate Aminotransferase

BL Baseline

BUN Blood urea nitrogen

COVID-19 Coronavirus disease 2019

CBC Complete Blood Count

CC50 Cytotoxic Concentration of 50%

CDC United States Centers for Disease Control

CMH Cochran-Mantel-Haenszel

CRF Case Report Form CRP C-reactive protein

CXR Chest X-ray

DSMB Data Safety Monitoring Board

EC Ethics Committee

EC50 50% Effective (Virus-Inhibitory)

ECG Electrocardiogram

EOS End of Study

EOT End of Treatment

FDA Food and Drug Administration

GCP Good Clinical Practice

G6PD Glucose 6-Phosphate Dehydrogenase

HIPAA Health Insurance Portability and Accountability Act

HR Hazard Ratio

ICH International Council for Harmonisation of Technical Requirements

for Registration of Pharmaceuticals for Human Use

IgG Immunoglobulin G
IgM Immunoglobulin M

INR International Normalized Ratio

IRB Institutional Review Board

K_i Inhibitory Constant

LDH Lactate Dehydrogenase

MedDRA Medical Dictionary for Regulatory Authorities

mITT modified Intent-to-Treat

Upamostat for Treatment of COVID-19 Amendment 4 15 June, 2021

NDA New Drug Application

PA Posterior Anterior

PCR Polymerase Chain Reaction

PP Per Protocol

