6.5 Laboratory Test Abnormalities

All new abnormal laboratory findings and those abnormal at baseline which change significantly (i.e., by at least one toxicity grade as defined in the National Cancer Institute Common Terminology Criteria for Adverse Events [NCI CTCAE] v5.0) are considered AEs. Laboratory AEs for which there is no clinical intervention will be recorded only on the laboratory data pages of the eCRF. Laboratory AEs not listed in the NCI CTCAE v5.0 will be considered as grade 1 (mild) if there is no clinical effect or intervention. Laboratory values outside the normal range for certain parameters will not be considered AEs if they are generally not considered as indicating an abnormality; this includes such parameters as liver enzymes which are below the normal range. If there is a clinical sequela or intervention, the laboratory abnormality is to be graded according to the criteria used for clinical AEs, described above.

The NCI CTCAE v5.0 can be downloaded in pdf format at:

https://ctep.cancer.gov/protocolDevelopment/electronic_applications/docs/CTCAE_v5_Quick_Reference_8.5x11.pdf

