7.4.2 Analysis of the secondary efficacy endpoints

Comparison between active treatment and placebo of the following secondary efficacy endpoints will be performed:

- 1) Incidence of hospitalization or death: the primary assessment of this endpoint will be among patients in the high risk group. This has been defined preliminarily above. The group may be redefined and recruitment restricted based on analysis at the end of part A and again in the interim analysis of part B. Additional secondary endpoints include:
- 2) The proportion of patients who are PCR-negative at each time point assessed, days 8, 15, 29 and 57 from the start of treatment (landmark analysis);
- 3) Time to resolution of individual disease-related symptoms present at baseline;
- 4) Development of new disease-related symptoms or pneumonia on study:

5) Changes in laboratory markers of disease severity, i.e., oxygen saturation, CRP, lymphocyte count and D-dimer levels, from baseline to time points at which these are measured on study;

The time frame for all endpoints unless otherwise stated is from Day 1 (day of first dose of study medication) through study Day 57. The time to event endpoints will be analyzed using the methods described for the primary endpoint above.

Binary (Yes/No) endpoints (development of pneumonia, hospitalization and mortality) will be summarized using counts and percentages for each group. A 95% confidence interval will be constructed for each proportion. Population-level risk differences will be used to estimate treatment effect. More specific details will be provided in the SAP.

Changes from baseline in continuous variables will be summarized by descriptive statistics and analyzed using repeated-measures model. Data will be log transformed, as needed.

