7.5.2 Clinical Safety Laboratory Tests

Laboratory tests and change from baseline at each time point will be tabulated by treatment groups. No inferential testing will be performed to compare the differences between the treatment groups.

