## 7. Data and Safety Monitoring Board Meeting Scope and Time Point

A data and safety monitoring board (DSMB) will be convened for oversight of the study. A DSMB charter is maintained as a separate document.

**Preliminary review**: The DSMB will be informed by the Sponsor on an ongoing basis of each patient whose study medication dose is reduced or discontinued due to toxicity. DSMB members may request an early review of all patients if warranted by the type, severity or frequency of toxicities resulting in dose reduction or drug discontinuation.

Study: RHB-107-01 Part A Statistical Analysis Plan (Version 2.0) **Initial full review**: The DSMB will review data after the first 60 patients have completed treatment and follow-up (part A), with regard to the following:

- a) Adverse events requiring dose modification or discontinuation of treatment overall and those considered at least possibly related to study medication;
- b) Serious adverse events deemed at least possibly related to study medication;
- c) Serious adverse events of any cause;
- d) Exacerbation of COVID-19 disease, including hospitalization;
- e) Effect of treatment on oxygen saturation, C-reactive protein, lymphocyte count and D-dimer (pharmacodynamic markers);
- f) Additional efficacy parameters available at that time, including time to sustained recovery, as defined above.

In addition to the safety data, proportions of subjects screened, enrolled, and length of follow-up will be provided by site for the Enrolled Population. Screening failure reasons will be summarized. Furthermore, subject disposition based on the Randomized Analysis Population, including subject status. Dose administration status overall and by treatment arm will be provided for the Safety Population.

Baseline information, demographics, treatment status, primary reason for early termination, and baseline laboratory values will be tabulated and summarized for the Safety Population.

A statistically significant difference in any of these parameters is unlikely with a limited early data set. However, the DSMB in conjunction with the sponsor will determine using their clinical judgement if, based on the safety profile of the two active arms, the tolerability is substantially lower at 400 mg as compared to 200 mg daily.

- A. If the DSMB determines that safety of both dose levels is similar, accrual in part B will proceed with the 400 mg daily schedule.

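### As read, Table 1 schedules no baseline CBC, biochemistry, INR or PTT, yet the lymphocyte endpoint, the laboratory change tables and the laboratory adverse event definition all need one

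*Protocol*

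**What the plan says.** The protocol synopsis (Methodology) refers to Table 1 for the timing of safety-laboratory and pharmacodynamic blood samples. In Table 1 the row beginning "CBC, biochem profile", which also names D-dimer, INR and PTT, is marked at days 8, 15, 29 and 57. Its baseline cell is empty. The next row, "CRP, D-dimer, troponin, ferritin", is marked on the same four days and also at baseline.

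Elsewhere the plan takes a baseline value for the first row's tests as given:

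- Protocol section 7.4.2 makes change in disease-severity markers a secondary endpoint, including "lymphocyte count and D-dimer levels, from baseline to time points at which these are measured on study". Protocol section 2 and SAP sections 2.2 and 13 carry the same endpoint. Protocol section 1.3 says lymphocyte counts are followed in every patient.
- Protocol section 7.5.2, repeated in SAP section 16.1: "Laboratory tests and change from baseline at each time point will be tabulated by treatment groups".
- Protocol section 6.5 treats as adverse events "All new abnormal laboratory findings and those abnormal at baseline which change significantly", where a significant change means at least one CTCAE grade. SAP section 15 repeats the rule.
- Protocol Table 2 (section 4.2.3) judges recovery from a held toxicity against the patient's baseline.
- SAP section 7, on the part A DSMB review, states that "baseline laboratory values will be tabulated and summarized for the Safety Population".

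**The concern.** The schedule and the analyses do not fit together. If sites follow Table 1 literally, the first CBC, chemistry, INR and PTT results are obtained after about a week of study drug. Lymphocyte change, which comes from the CBC, then has no starting point, and neither does change in any safety analyte other than D-dimer. The laboratory adverse event rule also loses its reference. It separates new abnormalities from those already present, in patients whose acute illness may itself have disturbed the blood count or chemistry before the first dose.

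The tests concerned matter for this drug. Protocol section 1.2 reports transaminase increases in a multidose volunteer study, and more grade 3 or 4 anemia at 400 mg than at 200 mg or in controls. Hemoglobin comes from the CBC, and ALT and AST from the biochemistry profile.

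**Working it through.** No sample size, power or alpha figure is involved. The check reads the schedule cell by cell and then looks for any other instruction to draw these tests before treatment.

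**1. Table 1, nine columns (BL, 1, 3, 8, 15, 22, 29, 43, 57).** Both laboratory rows have nine cells.

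| Row | Marked at | Draws |
|---|---|---|
| CBC, biochemistry, D-dimer, INR, PTT | 8, 15, 29, 57 | 4 |
| CRP, D-dimer, troponin, ferritin | BL, 8, 15, 29, 57 | 5 |

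The four shared marks line up, so the rows differ only in the baseline cell. D-dimer appears in both rows with different schedules.

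**2. Other places that could order the draw.**

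- Table 1, footnote d: "initial procedures include signing informed consent, review of medical history, review of documentation of COVID-19 disease and source/exposure, if available, height", followed by the pregnancy test. No blood count, chemistry or coagulation test is named.
- Table 1, biochemistry footnote: "Biochemistry profile to include, at a minimum, albumin, alkaline phosphatase, ALT, AST, bilirubin (total", then further analytes. It gives content, not timing.
- Protocol section 5.2: no baseline safety bloods are described.
- Protocol sections 3.1 and 3.2: no eligibility criterion uses a blood count, chemistry or clotting result, so screening does not force the sample either.

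**3. Timing of the first value.** Day 8±2 runs from day 8 − 2 = 6 to day 8 + 2 = 10. Treatment starts on day 1, so the value is always on treatment and cannot stand in for a baseline.

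**4. Effect on each analysis.**

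- *Change scores.* Lymphocyte change and safety-laboratory change are value at visit minus value at baseline. Without the second term they do not exist. Levels at days 8 to 57 can still be compared between arms.
- *Laboratory adverse events.* Under SAP section 15, events without clinical intervention are abstracted from the laboratory data, so the baseline value itself decides whether an event is counted. That section imputes no missing data, and neither document says how to classify an abnormal value that has no baseline.

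**5. Direction of the error.** Suppose every on-treatment abnormality is counted as new. Let *p* be the probability that an abnormality was already present and persists unchanged, and *a* the probability of a truly new one in a given arm, independent of *p*. The counted rate is *p* + (1 − *p*)*a*. For two arms with the same *p*, the difference is (1 − *p*)(*a*₁ − *a*₂). Each arm's rate is inflated, and the difference between arms is diluted rather than pushed toward either dose. The documents give no value for *p*, so the inflation cannot be sized.

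**The case against.** The strongest objection is that the point rests on one empty cell in a table read from a PDF. Matching cell counts exclude a shifted column but not a lost mark, and the same table shows other damage: the study-medication row has lost its content. Footnote d is also weak corroboration, because it omits the swab, ECG, CRP and antibody samples that Table 1 does mark at baseline. Moreover, the analyses and the SAP's DSMB section presuppose that baseline values exist, which points to a slip in the table rather than a deliberate omission. All of this stands, and it is why the first step must be to look at the original table. It does not remove the conflict: as read, the schedule omits a draw that the analyses need, and no sentence supplies it.

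A reader might go further and infer that the gap biases the choice between 200 and 400 mg, for instance because with 20 patients per arm one misclassified patient moves an arm's rate by 1/20 = 5 percentage points. The documents do not support that. The 5 points is only the weight of one patient, not an estimate of error. The same rule applies to all randomized, blinded arms. Overall laboratory event counts are not among the DSMB's listed items (protocol section 4.8, SAP section 7), which cover events leading to dose modification or discontinuation, serious events, COVID-19 exacerbation, pharmacodynamic markers and efficacy. Pharmacodynamic markers, lymphocytes included, are expressly not used for dosing, and the laboratory change tables are second tier (SAP section 16.1). Some influence remains, because adverse events are first tier (SAP section 2.2) and the DSMB judges safety overall, but it is indirect.

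Nor do the documents show that part A baseline samples were not taken. They show only that Table 1, as read, does not schedule them.

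**Conclusion.** The inconsistency is real and should be corrected. If the baseline cell is truly blank and sites follow it, no patient has a pre-treatment CBC, chemistry, INR or PTT value. Lymphocyte change and safety-laboratory change then cannot be computed as planned, and new laboratory adverse events cannot be separated from pre-existing abnormalities. D-dimer change is not lost, because the next row provides a baseline draw.

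The consequence is extra noise and inflated absolute laboratory event rates in all arms, not an advantage for one dose. This assumes that abnormal values without a baseline would be counted as new, and that persistence of a pre-existing abnormality does not itself depend on dose. The amount cannot be estimated from the documents. Table 2's reference to baseline has the same gap for blood count and chemistry toxicities, and those passages must be reconciled.

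**What to change.** 1. Check the baseline cell in the original Table 1. If the mark is there, only footnote d needs to name the sample.
2. If it is blank, mark CBC, biochemistry, INR and PTT at baseline. The row goes from 4 draws to 5 and matches the row below.
3. Reconcile the two D-dimer entries. Section 1.3 requires D-dimer in all patients, but its only baseline mark is in the row whose other analytes (CRP, troponin, ferritin) are limited to certain territories.
4. For part A, confirm whether baseline samples were taken. If not, state in the SAP or the part A report how laboratory changes and laboratory adverse events are classified without them.

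The cost is extra tubes at a baseline visit where blood is already drawn for D-dimer and antibodies, the added assays, and a table correction. No sample size, power or alpha figure changes.

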1.1 COVID-19 Disease

COVID-19 is a disease caused by a coronavirus, SARS-CoV-2. The disease was first noted in December 2019, in Wuhan, China, and subsequently attributed to a virus similar to the SARS coronavirus and now designated SARS-CoV-2. The clinical spectrum of SAR-CoV-2 infection ranges from asymptomatic infection to fatal pneumonia and multiorgan failure (Zhou et al, 2020). Many organ systems, including prominently gastrointestinal and neurological, as well as cardiorespiratory, may be affected. Infected individuals may be infectious for one to three days before onset of symptoms; up to half of new cases may be transmitted during that asymptomatic period (Gandhi et al, 2020). Common symptoms, with their incidence on presentation in the 191 patients in the initially reported severe Wuhan cohort were fever (94%), cough (79%), sputum production and fatigue (each 23%) and myalgia (15%). Bilateral pulmonary infiltrates were noted in 75% of patients on chest X-ray. In many patients, the illness is quite mild, with only a mild sore throat or upper respiratory tract symptoms, without fever.

In a large series from China, 81% of patients diagnosed with COVID-19 disease had mild cases (Wu and McGoogan, 2020). Over the past year, information on milder COVID-19 disease has been obtained (Ghandi et al, 2020; Han et al, 2020). Han and colleagues noted in particular that a large group of patients with mild COVID-19 disease has only gastrointestinal symptoms or a combination of gastrointestinal and mild pulmonary symptoms. Thus, the majority of patients have mild disease, and the spectrum of abnormalities appears to be different from that of severe COVID-19. Data from the Centers for Disease Control (CDC) show that as of mid-September, 2020, the overall incidence of confirmed or probable SARS-CoV-2 infection was approximately 2,000 per 100,000 population in the US; the overall incidence of hospitalization was 170 per 100,000. Thus, the hospitalization rate is under 10% of all confirmed and probable cases, i.e., the vast majority of COVID-19 patients are not hospitalized (CDC COVID Data Tracker).

People over age 65 and those with significant comorbidities, such as diabetes, obesity, or pulmonary disease, are more susceptible to severe infection, require hospitalization and have a higher mortality rate than do younger, otherwise healthy individuals. Men have an approximately 60% higher hospitalization or death rate than women (Williamson et al, 2020; van Gerwen et al, 2021)

For most people, the disease is self-limited. Many patients with relatively mild-moderate symptoms have now been diagnosed based on PCR as having SARS-CoV-2 infection. The majority of patients with COVID-19 symptoms are told to self-isolate, rest, and take symptomatic medications. But a major danger of the disease is spread through a generally nonimmune population, with infection of those who are at risk of severe infection. SARS-CoV-2 is highly contagious, with spread by aerosol and surface contact (van Doremalen et al, 2020) and potentially through stool (Wang et al, 2020). As the disease was first noted about a year and a half ago and testing and interpretation of data take some time, the clinical picture is still evolving. To date, no oral medication has demonstrated efficacy against SARS-CoV-2 infection of any severity. Monoclonal antibody combinations directed against the virus have shown preliminary evidence of efficacy in outpatient studies. However, certain SARS-CoV-2 strains have demonstrated resistance to some of the antibodies. In addition, these antibodies are

CONFIDENTIAL: PROPRIETARY INFORMATION

not available in many areas and, when available, are not always well accepted by patients. Thus, an effective, low toxicity oral medication will fulfill a major unmet medical need.

1.2 Upamostat

Upamostat, WX-671, is an orally bioavailable prodrug of WX-UK1, a serine protease inhibitor which inhibits several proteases in families which are involved in cleavage of the S-protein of coronaviruses. Cleavage of viral S-protein is important for viral binding and subsequent entry into host cells (Abe et al, 2013; Bertram et al, 2011; Zmora et al, 2018). In particular, WX-UK1 inhibits trypsin isoenzymes with Ki's of 19-190 nM, and several other related enzymes with Ki's under 1 μ M (Oldenburg et al, 2018). In addition, trypsin and other enzymes are upregulated in inflammatory lung conditions (Tsujimura et al, 2005; Yamada et al, 2006). Inhibiting these serine proteases may, in addition to a direct antiviral effect, also decrease tissue damage from the virus.

Two in vitro studies have demonstrated that upamostat inhibits SARS-CoV-2 infection (data on file, RedHill Biopharma, Ltd).

Upamostat inhibited entry of vesicular stomatitis virus transduced with the SARS-CoV-2 spike protein (VSVpp+SARS-2-S Δ18). When tested against VSVpp+SARS-2-S Δ18 in Calu3 cells, which have surface TMPRSS2, upamostat showed moderate inhibitory activity, though somewhat less than camostat, another serine protease inhibitor. Interestingly, when tested in Vero76 cells, which do not express surface TMPRSS2, moderate activity was still noted; camostat was inactive in this situation. Upamostat also had similar activity in native VSV infecting Calu3 cells as they did against S-protein transfected VSV. Again, in this setting camostat was inactive. All three compounds were inactive against native VSV infection in Vero76 cells. These results demonstrate activity and suggest that the activity may not be due solely to TMPRSS2. Due to the nature of the model, specific extrapolation to actual in vitro or in vivo inhibitory concentrations is not possible.

Upamostat was studied in a tissue culture model of primary human bronchial epithelial cells (HBEC; EpiAirway $^{\text{TM}}$, MatTek). Camostat was included for comparison and remdesivir was included as a positive control (Pruijssers et al., 2020).. A 3-log reduction in TCID50 was noted at the lowest concentration of upamostat tested, 0.12 µg/mL, rising to 4.5-log reduction at 1 µg/mL. Cytopathic effects were noted only at 30 µg/mL. At equal concentrations, the virus inhibitory effect of upamostat was somewhat greater than that of camostat, while the cytopathic effects were similar for both compounds.

Upamostat has been studied in 40 healthy volunteers and 152 cancer patients in phase 1 and phase 2 studies. Once daily dosing with 200 or 400 mg daily upamostat resulted in WX-UK1 tissue levels ≥0.6 µM (0.4 µg/gm tissue) in most patients and ≥1.0 µM (0.67 µg/gm tissue) in 6 of 10 patients studied (Meyer et al, 2008). Several-fold higher levels of WX-UK1 were found in stool after single doses of upamostat, which may be important given the possible fecal excretion of the virus. The drug was very well tolerated as a single agent and in combination with cytotoxic agents. In a multidose phase 1 study in healthy volunteers, upamostat caused some increases in transaminases, but not to a level to be considered problematic per Hy's law, nor were there changes in bilirubin. In addition, there was no dose-response relationship. In randomized phase 2 studies in cancer patients, in which all patients received a standard agent (either capecitabine or

gemcitabine) in combination with upamostat or control/placebo, there was no transaminase safety signal. Grade 3 or 4 anemia was more common at the 400 mg daily dose of upamostat than in patients receiving 200 mg daily or in the control groups. Other than that, there was no safety signal in the adverse event profiles in the phase 2 studies. Interestingly, in the breast cancer study, but not in the pancreatic cancer study, the incidence of grade 3 or 4 vascular events was 10% lower in patients receiving upamostat than in those receiving placebo.

